6.2 Dose modifications

6.2.1 Dose modification and dose delay

For patients who do not tolerate the protocol-specified dosing schedule, dose adjustments are permitted in order to allow the patient to continue the study treatment. Any changes in LDK378 administration must be recorded on the Dosage Administration Record eCRF.

LDK378 dose modification guidelines are described in [Section 6.2.3](#) and [Table 6-3](#). Any planned variance from these guidelines in view of patient safety must first be discussed with the sponsor unless there is an urgent need for action.

All dose modifications, interruptions or discontinuations must be based on the worst preceding toxicity as graded by the NCI Clinical Toxicity Criteria (NCI-CTCAE version 4.03).

General guidelines for dose modifications for toxicities other than those listed in [Table 6-3](#)

For grade 1 and tolerable grade 2 treatment related toxicities, patients may continue at the current dose of study treatment. For intolerable grade 2 or grade 3 treatment-related toxicities, dosing should be interrupted until at least resolution to grade 1 followed by dose reduction. For any grade 4 toxicity, patients should interrupt study treatment until resolution to at least grade 1, followed by either dose reduction or treatment discontinuation. Treatment with the study drug may subsequently be continued at a reduced dose level if in the opinion of the investigator the patient continues to experience clinical benefit and after discussion with the sponsor.

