Isolated elevations of any grade	Maintain dose level
Total Bilirubin** (for patients with Gilbert Syndrome these dose modifications apply to changes in direct [conjugated] bilirubin only)	
Grade 1 ($> ULN$ and $\leq 1.5 \times ULN$)	Maintain dose level with LFTs*** monitored as per protocol
Grade 2 (> 1.5 and $\leq 3.0 \times ULN$) with ALT or AST $\leq 3.0 \times ULN$	Omit dose until resolved to \leq Grade 1, then: If resolved in ≤ 7 days, then maintain dose level If resolved in > 7 days, then $\downarrow 1$ dose level

[figure not shown]
Grade 3 (> 3.0 and ≤ 10.0 x ULN) with ALT or AST ≤ 3.0 x ULN	Omit dose until resolved to ≤ Grade 1, then: If resolved in ≤ 7 days, ↓ 1 dose level If resolved in > 7 days discontinue patient from LDK378
Grade 4 (> 10.0 x ULN)	Permanently discontinue patient from LDK378
AST or ALT	
Grade 1 (> ULN and ≤ 3.0 x ULN)	Maintain dose level with LFTs*** monitored per protocol
Grade 2 (> 3.0 and ≤ 5.0 x ULN) without total bilirubin elevation to > 2.0x ULN	Maintain dose level with LFTs*** monitored per protocol
Grade 3 (> 5.0 and ≤ 20.0 x ULN) without total bilirubin elevation to > 2.0 x ULN	Omit dose until resolved to ≤ Grade 1 (or to baseline) then ↓ 1 dose level
Grade 4 (> 20.0 x ULN) without total bilirubin elevation to > 2.0 x ULN	Omit dose until resolved to ≤ Grade 1 (or to baseline) then ↓ 1 dose level
AST or ALT and concurrent Total Bilirubin	
AST or ALT > 3.0 x ULN and total bilirubin > 2.0x ULN in the absence of cholestasis or hemolysis	Permanently discontinue patient from LDK378. Refer to Section 6.2.4.2 for additional follow-up
PANCREATIC	
Amylase and/or lipase elevations (in the absence of clinical symptoms)	
Grade 1 (> ULN and ≤1.5 x ULN)	Maintain dose level
Grade 2 (>1.5 - 2.0 x ULN)	Maintain dose level
Grade ≥3 (> 2.0 x ULN)	Omit dose until resolved to ≤ Grade 1, then ↓ 1 dose level
Note: Withhold LDK378 for acute onset of new or progressive unexplained abdominal symptoms, such as severe pain or vomiting; perform diagnostic procedures (e.g., abdominal CT scan or ultrasound) to exclude pancreatic pathology.	
RENAL	
Serum creatinine	
Grade 1 (>1 and ≤1.5 x baseline; >ULN -1.5 x ULN)	Maintain dose level
Grade 2 (>1.5 and ≤3.0 x baseline; > 1.5 -3.0 x ULN)	Omit dose until resolved to ≤ Grade 1, then: If resolved in ≤ 7 days, then maintain dose level If resolved in > 7 days, then ↓ 1 dose level
Grade 3 (>3.0 x baseline; > 3.0 - 6.0 x ULN)	Omit dose until resolved to ≤ Grade 1, then ↓ 1 dose level

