** If Grade 3 or 4 hyperbilirubinemia is due to the indirect (non-conjugated) component only, and hemolysis as the etiology has been ruled out as per institutional guidelines (e.g., review of peripheral blood smear and haptoglobin determination), then ↓ 1 dose level and continue treatment at the discretion of the investigator.

***LFTs include albumin, ALT, AST, total bilirubin (fractionated if total bilirubin > 2.0 x ULN), alkaline phosphatase and GGT

**** Dose modifications apply to patients who experience diarrhea despite appropriate antidiarrheal medication. This medication should be started at the first sign of abdominal cramping, loose stools or overt diarrhea (see [Section 6.2.4.4](#))

***** Dose modifications apply to patients who experience nausea and/or vomiting despite appropriate antiemetic medication. This medication should be started at the first sign of nausea and/or vomiting (see [Section 6.2.4.5](#))

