- For patients with elevated AST or ALT or TBIL value at baseline: [AST or ALT $> 2 \times$ baseline AND $> 3.0 \times$ ULN] OR [AST or ALT $> 8.0 \times$ ULN], combined with [TBIL $> 2 \times$ baseline AND $> 2.0 \times$ ULN]

Medical review needs to ensure that liver test elevations are not caused by cholestasis, defined as: ALP elevation $> 2.0 \times$ ULN with R value (ALT/ALP in \times ULN) < 2 in patients without bone metastasis, or elevation of ALP liver fraction in patients with bone metastasis.

Note: (The R value is calculated by dividing the ALT by the ALP, using multiples of the ULN for both values. It denotes the relative pattern of ALT and/or ALP elevation is due to cholestatic or hepatocellular liver injury).

In the absence of cholestasis, these patients should be immediately discontinued from study drug treatment, and repeat LFT testing as soon as possible, preferably within 48 hours from the awareness of the abnormal results. The evaluation should include laboratory tests, detailed history, physical assessment and the possibility of liver metastasis or new liver lesions, obstructions/compressions, etc.

- Laboratory tests should include ALT, AST, albumin, creatinine kinase, total bilirubin, direct and indirect bilirubin, GGT, prothrombin time (PT)/INR and alkaline phosphatase.

- A detailed history, including relevant information, such as review of ethanol, concomitant medications, herbal remedies, supplement consumption, history of any pre-existing liver conditions or risk factors, should be collected.
- Further testing for acute hepatitis A, B, C or E infection and liver imaging (eg, biliary tract) may be warranted.

- [REDACTED]
- Additional testing for other hepatotropic viral infection (CMV, EBV or HSV), autoimmune hepatitis or liver biopsy may be considered as clinically indicated or after consultation with specialist/hepatologist.

All cases confirmed on repeat testing meeting the laboratory criteria defined above, with no other alternative cause for LFT abnormalities identified should be considered as “medically significant”, thus, met the definition of SAE ([Section 8.2.1](#)) and reported as SAE using the term “potential drug-induced liver injury”. All events should be followed up with the outcome clearly documented.

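### Table 6-3 mishandles two hepatic combinations when both ALT and AST exceed 3.0 x ULN: one keeps the dose where milder liver tests require a hold, and one, with cholestasis, has no dose action

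*Protocol*

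**What the plan says.** The hepatic part of Protocol Table 6-3 (Section 6.2.3) ties bilirubin rows to transaminases and transaminase rows to bilirubin. All values below are multiples of ULN.

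- **Total bilirubin.** Grade 2 (above 1.5 to 3.0) means omit, then resume at the same or a lower dose depending on whether it resolves within 7 days. Grade 3 means omit, then reduce or discontinue. Both rows carry a transaminase condition; the Grade 3 row reads "Grade 3 (> 3.0 and ≤ 10.0 x ULN) with ALT or AST ≤ 3.0 x ULN". Grade 4 (above 10.0) means discontinue, with no condition.
- **AST or ALT.** The Grade 2 row reads "Grade 2 (> 3.0 and ≤ 5.0 x ULN) without total bilirubin elevation to > 2.0x ULN" and maintains the dose. Grades 3 and 4, with the same bilirubin condition, mean omit and then reduce.
- **Combined row.** AST or ALT above 3.0 with bilirubin above 2.0 means permanent discontinuation, but only "in the absence of cholestasis or hemolysis".
- **Footnote \*\*.** "If Grade 3 or 4 hyperbilirubinemia is due to the indirect (non-conjugated) component only", and hemolysis has been ruled out (for example by "review of peripheral blood smear and haptoglobin determination"), the dose is reduced one level and treatment continues at the investigator's discretion.

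Section 6.2.4.2 sets thresholds for possible drug-induced liver injury that depend on baseline values, and then states: "In the absence of cholestasis, these patients should be immediately discontinued from study drug treatment". It defines cholestasis as ALP above 2.0 with an R value below 2 in patients without bone metastasis, "or elevation of ALP liver fraction in patients with bone metastasis".

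**The concern.** A dose-modification table should give every combination an action, and worse liver tests should not earn a milder one. The cross-conditions break both properties. The bilirubin Grade 2 row starts at 1.5 but the combined row starts at 2.0. In between, a patient whose two enzymes are both above 3.0 leaves the bilirubin row without reaching the combined row. Above 2.0, cholestasis switches off the combined row, and no other row takes its place when both enzymes are above 3.0.

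A site that follows the table would keep dosing in the first case and have no stated dose action in the second. Hepatotoxicity is an adverse event of special interest (Protocol 8.1.3), and Grade 3/4 ALT increase was reported in 26.7% of patients at 750 mg in the phase I study (Table 1-1). Enzymes above 3.0 are therefore not remote, although their joint frequency with raised bilirubin is not given.

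**Working it through.** The plan gives no figure to reproduce here, so the check is a literal reading of the table's logic. Assumptions: the bilirubin Grade 2 and 3 condition is met if either enzyme is at most 3.0; the AST/ALT grade follows the worse enzyme; the combined row needs both cholestasis and hemolysis absent. Gilbert syndrome, for which the bilirubin rows use direct bilirubin, is left aside.

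**Cell (a), the reversal**

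| Bilirubin | ALT / AST | Bilirubin Grade 2 row | AST/ALT row | Combined row | Action |
|---|---|---|---|---|---|
| 1.8 | 2 / 2 | applies: omit | Grade 1: maintain | no | **omit** |
| 1.8 | 4 / 4 | fails, no enzyme ≤ 3.0 | Grade 2: maintain | no, bilirubin ≤ 2.0 | **maintain** |

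If the worse enzyme is above 5.0, the AST/ALT Grade 3 or 4 row gives omit then reduce, so the reversal is confined to both enzymes above 3.0 to 5.0 and bilirubin above 1.5 to 2.0.

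**Cell (b), the gap.** Take bilirubin 2.5, ALT and AST 4, ALP 2.5, no bone metastasis. R = 4 / 2.5 = 1.6, below 2, and ALP is above 2.0, so this is cholestasis under Section 6.2.4.2.

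- Bilirubin Grade 2 row: fails, because neither enzyme is at most 3.0.
- AST/ALT Grade 2 row: fails, because bilirubin is above 2.0.
- Combined row: fails, because cholestasis is present.
- Section 6.2.4.2: orders discontinuation only without cholestasis.

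The same holds up to bilirubin 10.0; above that the bilirubin Grade 4 row applies.

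**Extent in the table.** The grid has 6 bilirubin bands (≤1, >1–1.5, >1.5–2, >2–3, >3–10, >10), 5 bands each for ALT and AST (≤1, >1–3, >3–5, >5–20, >20), cholestasis yes/no and hemolysis yes/no: 6 x 5 x 5 x 2 x 2 = 600 combinations.

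- Cell (a): 1 bilirubin band x 1 enzyme pair x 4 states = 4.
- No table row: 2 bilirubin bands x 9 enzyme pairs x 3 states (cholestasis only, hemolysis only, both) = 54.
- Of these, with cholestasis: 2 x 9 x 2 = 36. This is cell (b).
- Hemolysis only: 2 x 9 x 1 = 18. The table is silent, but Section 6.2.4.2 orders discontinuation when its thresholds are met, so these are not part of the gap.

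**Footnote \*\*.** Splitting each combination by purely indirect bilirubin yes/no doubles the 36 to 72. The footnote needs Grade 3 or 4 bilirubin, a purely indirect rise and no hemolysis, which leaves 1 bilirubin band x 9 enzyme pairs = 9 of the 72 with an action.

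**Effect of the row changes proposed below.** Rank the actions: maintain, bilirubin Grade 2 omit, AST/ALT Grade 3/4 omit then reduce, bilirubin Grade 3, discontinue. On the table rows alone, before footnote \*\* and Section 6.2.4.2 are applied, all 54 unmatched combinations obtain a row, 28 become stricter, none becomes milder and 518 are unchanged (54 + 28 + 518 = 600). The 28 are the 4 in cell (a) and 24 with bilirubin above 2.0 to 3.0, one enzyme above 5.0 and the other at most 3.0 (8 enzyme pairs x 3 states). In the 18 hemolysis-only combinations the new row action would be milder than the discontinuation in Section 6.2.4.2, so the fix has to let that section prevail.

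**The case against.** **Other text may supply the action.** The general rule in Section 6.2.1 interrupts and reduces, but its heading limits it to toxicities not listed in Table 6-3, and bilirubin and AST/ALT are listed. A site could argue that an unmatched combination is unlisted; the contrary reading is at least as natural, and the argument cannot reach cell (a), which does match a row. Section 6.2.2 covers resumption after toxicities the table does not describe. The instruction to act on the worst preceding toxicity does not help when that toxicity's own row condition fails.

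**Clinical judgment remains.** Section 6.2.1 says "Any planned variance from these guidelines in view of patient safety must first be discussed with the sponsor", with an exception for urgent need, and Section 7.1.4.1 tells the investigator to stop treatment judged detrimental. Weekly liver tests also apply. These soften the consequence and that part stands, but none states a dose action.

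**The Grade 2 AST/ALT rule was deliberate.** Amendment 3 chose to maintain the dose there and to act more strictly above bilirubin 2.0. That explains the 2.0 cut-off. It does not explain why the same bilirubin with lower enzymes needs a hold.

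**The counts carry little clinical weight.** This stands. Cholestasis is treated as independent of ALT, although R below 2 means that ALT above 20 needs ALP above 10 in patients without bone metastasis. The bands and the ranking of actions are choices of this review.

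**Stronger readings a reader might infer.** One is that hemolysis without cholestasis is equally uncovered, giving 54 rather than 36. Section 6.2.4.2 does not support that: it exempts only cholestasis. Its thresholds are higher for patients with abnormal baseline values, and baseline was not modelled, so it need not order discontinuation in every one of the 18. Another is to read the bilirubin condition as requiring both enzymes at or below 3.0. That would raise the no-row count to 126 and the reversals to 20, but the table says either enzyme, and the smaller counts are used here.

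**Conclusion.** Both defects are present in the current wording of Table 6-3. Cell (a) gives a milder action for worse liver tests. Cell (b) has no dose action in the table or in Section 6.2.4.2, apart from the small part reached by footnote \*\*. On the literal reading they occupy 4 and 36 of 600 grid combinations.

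This is a minor safety correction. The counts describe the table, not patients. The figure of less than 1% in Protocol 1.3 is for ALT above 3 and bilirubin above 2 with normal ALP; it covers neither cell (a), where bilirubin is at most 2.0, nor cholestasis defined by raised ALP. Nothing here supports a claim that patients were harmed, and the primary ORR test is unaffected. SAP 2.1 gives last patient last visit as 22-Jan-2018, so the benefit is limited to patients dosed before then and to protocols that reuse the table.

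**What to change.** 1. In the bilirubin Grade 2 and Grade 3 rows, delete the condition on ALT or AST.
2. In the AST/ALT Grade 2, 3 and 4 rows, delete the condition on total bilirubin.
3. State that when more than one hepatic row applies, or a Table 6-3 row and the discontinuation instruction in Section 6.2.4.2 both apply, the most restrictive action governs. A patient who meets the Section 6.2.4.2 criteria without cholestasis, including one with hemolysis, is then still discontinued.
4. State that footnote \*\* modifies only the bilirubin Grade 3 and 4 rows and never overrides an AST/ALT row, the combined row or Section 6.2.4.2.

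The combined row stays as it is. Results:

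- Bilirubin 1.8 with ALT and AST 4: omit.
- Bilirubin 2.5 with ALT and AST 4 and cholestasis: omit.
- Bilirubin 2.5 with ALT and AST 8 and cholestasis: omit, then reduce.
- Purely indirect bilirubin 4 with ALT 8, no cholestasis or hemolysis: permanent discontinuation.

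The cost is amendment wording and a site letter while patients are on treatment, or only a wording change where the table is reused later. The downside is some extra dose holds and reductions, including the 24 grid combinations with only one enzyme above 3.0, which move to omit then reduce unless Section 6.2.4.2 already requires discontinuation. For this trial, the liver-test listing planned in SAP 2.8.2 can identify cell (a) patients. It can identify cell (b) patients only in part, because it holds bilirubin, ALT, AST and ALP but not the hemolysis work-up or the ALP liver fraction.

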6.2.4 Follow-up for toxicities

An unscheduled visit should be performed in all cases below where toxicity monitoring is recommended more frequently than defined by the schedule of assessments (Table 7-1).

6.2.4.1 Guidelines for the follow-up of laboratory hematologic abnormalities

In case of any occurrence of febrile neutropenia, neutropenia \geq grade 3 or thrombocytopenia \geq grade 3, tests must be performed weekly (or more frequently if clinically indicated) until the event resolves to \leq grade 2. Subsequent monitoring must be performed every 4 weeks. See Table 6-4.

Table 6-4 Follow-up evaluations for selected toxicities

Toxicity	Follow-up evaluation*
Investigations (hematologic)	Febrile neutropenia, neutropenia or thrombocytopenia \geq CTCAE Grade 3 Test weekly (or more frequent) until \leq Grade 2 Subsequent monitoring must be performed every 4 weeks
Investigations (hepatic)	ALT/AST/total bilirubin Grade 2: Test weekly (or more frequent) until \leq Grade 1 Thereafter, continue to test every 2 weeks (or more frequent) for 2 cycles (8 weeks). If no recurrence of \geq Grade 2 event, continue monitoring every cycle (4 weeks) ALT/AST/total bilirubin \geq Grade 3: Test weekly (or more frequent) until \leq Grade 1 Thereafter, continue to test every 2 weeks (or more frequent) for 4 cycles (16 weeks). If no recurrence of \geq grade 2 event, continue monitoring every cycle (4 weeks) Discontinuation due to liver toxicity: Test weekly (or more frequent) until \leq Grade 1 or stabilization Patients with liver metastasis and grade 2 AST/ALT at baseline, increased monitoring is required; for grade 3 or 4 AST/ALT follow guidelines for grade 3 or 4 AST/ALT
Investigations (renal)	Serum creatinine Grade 2: Test weekly (or more frequent) until Grade 1 Thereafter, test every cycle (4 weeks) Serum creatinine \geq Grade 3: Test twice weekly (or more frequent) until \leq Grade 1 Thereafter, test every cycle (4 weeks)
Investigations (pancreatic)	Amylase/lipase \geq Grade 3: Test weekly (or more frequently) until \leq Grade 1. After resumption of dosing, continue to test weekly for one additional cycle (4 weeks). If no reoccurrence of \geq Grade 2 event, continue monitoring every cycle (4 weeks)
*Note: this table refers only to the evaluation schedule to monitor selected toxicities. Refer to Table 6-3 for dose modifications required for applicable toxicities	

6.2.4.2 Guidelines for the follow-up of laboratory liver abnormalities

In patients with any clinically relevant laboratory liver abnormality, as defined below, hepatic toxicity monitoring must include ALL of the following liver function tests (LFTs): albumin, ALT, AST, total bilirubin (fractionated if total bilirubin $>$ 2.0 x ULN), alkaline phosphatase and GGT. Note: for patients with Gilbert Syndrome, total and direct bilirubin must be monitored, but intensified monitoring applies to changes in direct bilirubin only.

In case of any occurrence of ALT/AST/total bilirubin increase to grade 2 the LFTs must be monitored weekly (or more frequently if clinically indicated) until the event resolves to \leq

grade 1. Thereafter monitoring must be continued every other week (or more frequently if clinically indicated) for two additional cycles (e.g. 8 weeks). If there is no recurrence of grade ≥ 2 ALT/AST/total bilirubin elevations during this period, subsequent monitoring must be performed every 4 weeks. For patients with liver metastasis and grade 2 AST/ALT at baseline, increased monitoring is required; for grade 3 and 4 AST/ALT; follow guidelines for grade 3 or 4 AST/ALT.

In case of any occurrence of ALT/AST/total bilirubin increase to grade 3 or 4, LFTs must be monitored weekly (or more frequently if clinically indicated) until the event resolves to \leq grade 1 or to baseline. Thereafter monitoring must be continued every other week (or more frequently if clinically indicated) for four additional cycles (e.g. 16 weeks). If there is no recurrence of \geq grade 2 ALT/AST/total bilirubin elevations during this period, subsequent monitoring must be performed every 4 weeks.

Patients who discontinue study treatment due to liver toxicity must be monitored weekly (or more frequently if clinically indicated) until the event resolves to \leq grade 1 or stabilization occurs (no CTCAE grade change over 4 weeks).

Refer to [Table 6-4](#).

Patients with transaminase increase combined with total bilirubin (TBIL) increase may be indicative of potential DILI, and should be considered as clinically important events.

The threshold for potential DILI may depend on the patient's baseline AST/ALT and TBIL value; patients meeting any of the following criteria will require further follow-up as outlined below:

[figure not shown]
- For patients with normal ALT and AST and TBIL value at baseline: AST or ALT $> 3.0 \times$ ULN combined with TBIL $> 2.0 \times$ ULN
- For patients with elevated AST or ALT or TBIL value at baseline: [AST or ALT $> 2 \times$ baseline AND $> 3.0 \times$ ULN] OR [AST or ALT $> 8.0 \times$ ULN], combined with [TBIL $> 2 \times$ baseline AND $> 2.0 \times$ ULN]

Medical review needs to ensure that liver test elevations are not caused by cholestasis, defined as: ALP elevation $> 2.0 \times$ ULN with R value (ALT/ALP in \times ULN) < 2 in patients without bone metastasis, or elevation of ALP liver fraction in patients with bone metastasis.

Note: (The R value is calculated by dividing the ALT by the ALP, using multiples of the ULN for both values. It denotes the relative pattern of ALT and/or ALP elevation is due to cholestatic or hepatocellular liver injury).

In the absence of cholestasis, these patients should be immediately discontinued from study drug treatment, and repeat LFT testing as soon as possible, preferably within 48 hours from the awareness of the abnormal results. The evaluation should include laboratory tests, detailed history, physical assessment and the possibility of liver metastasis or new liver lesions, obstructions/compressions, etc.

- Laboratory tests should include ALT, AST, albumin, creatinine kinase, total bilirubin, direct and indirect bilirubin, GGT, prothrombin time (PT)/INR and alkaline phosphatase.

- A detailed history, including relevant information, such as review of ethanol, concomitant medications, herbal remedies, supplement consumption, history of any pre-existing liver conditions or risk factors, should be collected.
- Further testing for acute hepatitis A, B, C or E infection and liver imaging (eg, biliary tract) may be warranted.

- [REDACTED]
- Additional testing for other hepatotropic viral infection (CMV, EBV or HSV), autoimmune hepatitis or liver biopsy may be considered as clinically indicated or after consultation with specialist/hepatologist.

All cases confirmed on repeat testing meeting the laboratory criteria defined above, with no other alternative cause for LFT abnormalities identified should be considered as “medically significant”, thus, met the definition of SAE ([Section 8.2.1](#)) and reported as SAE using the term “potential drug-induced liver injury”. All events should be followed up with the outcome clearly documented.

